## **Avapritinib**

### **Statistical Analysis Plan Study BLU-285-1303**

16. AE related to study drug by PT and NCI CTCAE Grade
17. AE related to study drug by SOC, PT, and NCI CTCAE Grade
18. SAE by PT and NCI CTCAE Grade
19. SAE by SOC, PT, and NCI CTCAE Grade
20. SAE related to study drug by PT and NCI CTCAE Grade
21. AE leading to interruption of study drug by SOC and PT
22. AE leading to interruption of study drug by PT
23. AE leading to dose reduction of study drug by SOC and PT
24. AE leading to dose reduction of study drug by PT
25. AE leading to permanent discontinuation of study drug by SOC and PT
26. AE leading to permanent discontinuation of study drug by PT
27. AE related to study drug leading to interruption of study drug by PT
28. AE related to study drug leading to dose reduction of study drug by PT
29. AE related to study drug leading to permanent discontinuation of study drug by PT

All AEs will be listed by patient.

Subgroup analyses will be conducted for items 1 – 13 above (details in [Table 4](#)) in the Safety Population.

#### **4.7.2 Adverse Events of Special Interest**

Adverse events of special interest (AESI) will be summarized by category (cognitive effects and intracranial bleeding) and relevant PTs.

- Cognitive effects consisting of 4 PTs: cognitive disorder, memory impairment, confusional state, encephalopathy
- Intracranial bleeding consisting of 3 PTs: haemorrhage intracranial, cerebral haemorrhage, subdural haematoma.

The general rules for summarizing AE specified in [Section 4.7.1](#) apply for AESIs for avapritinib. The following AESI tables will be presented:

- AESI by AESI category and PT
- AESI related to study drug by AESI category and PT
- Serious AESI by AESI category and PT
- Serious AESI related to study drug by AESI category and PT
- Grade 3/4/5 AESI by AESI category and PT

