Treatment with avapritinib has been well tolerated in patients with GIST. Most AEs have been Grade 1 or 2 in intensity, with the most common ( $\geq 25\%$ ) including nausea (56%), fatigue (53%), periorbital edema (43%), vomiting (41%), peripheral edema (34%), anemia (31%), diarrhea (31%), cognitive effects (consisting of multiple similar AEs aggregated into a single category [30%]), increased lacrimation (30%), and decreased appetite (28%). There were no DLTs until the 600 mg dose cohort was reached and DLTs were noted in 2 patients: 1 patient experienced Grade 2 hypertension, Grade 2 rash, and Grade 2 memory impairment; the other patient experienced Grade 2 hyperbilirubinemia. The maximum tolerated dose was determined to be 400 mg QD.

Overall, 49 patients discontinued avapritinib treatment. Six patients discontinued due to AEs, 40 patients discontinued due to disease progression, and 3 patients discontinued avapritinib due to patient's decision.

The single dose (Cycle 1 Day 1; C1D1) and steady state (Cycle 1 Day 15; C1D15) pharmacokinetics of avapritinib have been evaluated in Study BLU-285-1101. Preliminary unaudited PK data from the 11 April 2018 datacut are presented. After administration of single oral doses of avapritinib ranging from 30 to 400 mg avapritinib, the median time to peak concentration ( $T_{max}$ ) ranged from 2 to 4 hours postdose, and the mean plasma elimination half-life of avapritinib ranged from 35 hours to 57 hours. After a single dose and repeat dosing of avapritinib, systemic exposure was dose proportional over the dose range of 30 mg to 400 mg QD. The steady state (C1D15) geometric mean  $C_{max}$  (%CV) of avapritinib at doses of 300 mg QD and 400 mg QD was 774 ng/mL (49.4%) and 1009 ng/mL (50.9%), respectively, and the corresponding area under the plasma concentration-time curve ( $AUC_{0-\tau}$ ) was 14074 h•ng/mL (45.1%) and 20298 h•ng/mL (41.5%), respectively. The mean accumulation ratio after repeat dosing of avapritinib (dose range: 30 – 400 mg QD) was 3.4 – 5.2. Based on the data collected thus far, and the exposures required for antitumor activity in GIST patient-derived xenograft models (Figure 2), systemic exposure at 300 mg QD - 400 mg QD is predicted to provide broad coverage of the primary (eg, exon 11) and secondary KIT (eg, exon 11/17 and exon 11/13) mutations.

[figure not shown]
**Figure 2: Clinical Exposure of Avapritinib Reaches Levels Projected to be Efficacious Across Multiple KIT-mutant Genotypes**

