**Table 1: Dose Modification and Re-escalation Guidelines for Avapritinib-Related Toxicity**

Toxicity	Modification
General	
Grade 1 or Grade 2	
 
No dose modification required
 

Grade 3 - 4	
 
Occurrence: Hold until event is <math>\leq</math> Grade 2, or has returned to baseline, and then resume by reducing the dose by 100 mg less than the current dose 
 

 
 
 
Occurrence at 100 mg: Discontinue avapritinib 
 

 
 
 

Cognitive or Mood Effects	
Grade 1 with only minor impairment	No dose modification required
Grade 1, other than minor impairment	
 
Interrupt dosing for 7 days, and resume dosing without dose reduction
 
The dosing interruption may be repeated if the impairment continues to worsen after resuming dosing; however, repeated dosing interruption is at the discretion of the investigator, and should be balanced with the need to treat the underlying GIST
 

Grade 2	
 
Interrupt dosing for a minimum of 7 days
 
Resume dosing with a dose reduction of 100 mg when the cognitive effect has improved to Grade 1 or less, or still at Grade 2, if continued treatment is considered in the best medical interest of the patient due to the underlying GIST
 
If the patient is already receiving a dose of 100 mg QD, and continued treatment is considered in the best medical interest of the patient due to the underlying GIST, treatment may be resumed at 100 mg
 

Grade 3-4	
 
Interrupt dosing for a minimum of 14 days
 
Resume dosing with a dose reduction of 100 mg when the cognitive effect has improved to Grade 1 or less, or when it has improved to Grade 2, if continued treatment is considered in the best medical interest of the patient due to the underlying GIST
 
Occurrence at 100 mg: Discontinue avapritinib
 

Intracranial Bleeding	
Grade 1	
 
Interrupt dosing for a minimum of 7 days, and re-image the brain
 

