	
 
Resume dosing without dose reduction, if the bleed is stable or improving, and continued treatment is considered in the best medical interest of the patient due to the underlying GIST
 

Grade 2	
 
Interrupt dosing for a minimum of 14 days and re-image the brain
 
Resume dosing with a dose reduction of 100 mg when the intracranial bleeding has improved to Grade 1 or less, or still at Grade 2, if continued treatment is considered in the best medical interest of the patient due to the underlying GIST
 
Occurrence at 100 mg: Discontinue avapritinib
 

Grade 3-4	
 
Discontinue avapritinib
 

Abbreviations: CNS = central nervous system; GIST = gastrointestinal stromal tumor; QD = once daily.

 Changes in cognition, memory, attention, mood, or speech (thought to originate in the CNS).

 If avapritinib treatment is resumed after interruption for a cognitive or mood effect, or for an intracranial bleeding event, the investigator must document in writing that resuming avapritinib treatment was considered to be in the best medical interest of the patient.

For regorafenib, dose modification is described in [Appendix 2](#).

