### **9.1.3 Serious Adverse Event**

An AE is assessed as SAE if, in the view of either the Investigator or the Sponsor, it results in any of the following outcomes (seriousness criteria):

- **Death:** An AE that results in death.

NOTE: For AEs that result in 'death' the adverse event term describing the medical occurrence causing death should be reported with the outcome and seriousness criteria recorded as 'death'. Only if the cause of death is unknown and no other medical occurrence is suspected to have caused or contributed to 'death', 'death' should be used as adverse event term.

- **Life-threatening:** An AE is life-threatening.

NOTE: The term 'life-threatening' refers to an event in which the study patient was at risk of death at the time of the event; it does not refer to an event which hypothetically might have caused death if it was more severe.

- **Inpatient hospitalization or prolongation of existing hospitalization:** All AEs requiring hospitalization (in-patient or emergency department treatment) for more than 24 hours should be considered SAEs.

NOTE: Hospitalization for elective surgery or routine clinical procedures that are not the result of AE (eg, elective surgery for a pre-existing condition that has not worsened) should not be reported as AE or SAE. Any untoward medical occurrence in temporal relationship to the procedure, however, must be reported as an AE, either 'serious' or 'non-serious' according to protocol definitions.

- **Persistent or significant disability/incapacity:** An AE is incapacitating or disabling if the experience results in a substantial and/or permanent disruption of the patient's ability to carry out normal life functions.

- **Congenital anomaly/birth defect:** A fixed, permanent impairment in the offspring of a patient (or patient's partner) who received study treatment.
- **Medically important events:** Important medical events that may not result in death, be life-threatening, or require hospitalization may be considered an SAE when, based upon appropriate medical judgment, they may jeopardize the subject and may require medical or surgical intervention to prevent 1 of the outcomes listed in this definition. Examples of such events are:
  - Intracranial bleeding events. All events of intracranial bleeding should be reported as SAEs.
  - Intensive treatment in an emergency room or at home for allergic bronchospasm.
  - Blood abnormalities or convulsions that do not result in inpatient hospitalization.

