#### **9.4 Adverse Event Monitoring Period**

Adverse events will be recorded in the eCRF from the first dose of a study drug dose through 30 days after the last dose of any study drug. Serious AEs and serious pretreatment events (see [Section 9.9](#)) will be recorded in the eCRF from the time of signing informed consent through 30 days after the last study drug dose. In addition, SAEs that are assessed as related to study treatment that occur > 30 days post-treatment will also be reported. All related AEs and AEs relating to cognitive function and intracranial bleeding should be monitored until they are resolved, are stabilized, have returned to pre-exposure baseline, are determined to be due to another illness, or until a subsequent antineoplastic therapy is initiated, even if > 30 days post last dose of study drug. For AEs considered not related to study drug, similar monitoring guidelines will only be required through 30 days after the last dose of study drug.

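### The closed AESI lists (4 cognitive and 3 bleeding terms) are narrower than the protocol's description of these risks, so the AESI category rates could be understated.

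*SAP*

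**What the plan says.** SAP 4.7.2 sets up two categories: "Adverse events of special interest (AESI) will be summarized by category (cognitive effects and intracranial bleeding) and relevant PTs". Each is then given as a fixed list. The first is "Cognitive effects consisting of 4 PTs: cognitive disorder, memory impairment, confusional state, encephalopathy". The second is "Intracranial bleeding consisting of 3 PTs: haemorrhage intracranial, cerebral haemorrhage, subdural haematoma". Neither uses a standard MedDRA grouping, open-ended wording, or a review step for adding terms before database lock.

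The section plans nine AESI tables. Seven are by category and PT: all, related, serious, serious and related, Grade 3/4/5, related Grade 3/4/5, and by CTCAE grade. The other two, on permanent discontinuation, are by PT only.

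The protocol has no AESI definition, but it describes the same risks in three places:

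- Table 1 has a row group for cognitive or mood effects. Its footnote 1 describes them as "Changes in cognition, memory, attention, mood, or speech (thought to originate in the CNS".
- Section 9.1.3 says of bleeding: "All events of intracranial bleeding should be reported as SAEs".
- Section 9.4 extends follow-up for both risks: "All related AEs and AEs relating to cognitive function and intracranial bleeding should be monitored until they are resolved".

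**The concern.** The protocol handles a change in mood, speech or attention of central origin in the same row group as a memory or cognition event. The SAP counts special-interest events by a list in which those three domains are not named. A patient could therefore have an event managed under Table 1 and still not appear in the cognitive AESI category. Likewise, a bleed coded to a fourth PT would be an SAE under the protocol but not an AESI under the SAP.

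Cognitive effects and intracranial bleeding are the risks the protocol singles out, with dedicated rows in Table 1, brain imaging at Screening and Weeks 12 and 24, and follow-up beyond 30 days. At stake is how completely the category tables state their incidence, severity and seriousness. No hypothesis test, event count, power or alpha depends on these lists.

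**Working it through.** The plan states no figure that depends on the AESI lists, so there is nothing to reproduce. The check sets the texts side by side and adds one illustration.

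**1. Cognitive list against Table 1, footnote 1**

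| Domain in the footnote | SAP term naming it |
|---|---|
| Cognition | cognitive disorder (confusional state and encephalopathy are also listed) |
| Memory | memory impairment |
| Attention | none |
| Mood | none |
| Speech | none |

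Three of five domains have no named term. This matches words, not coding. The documents do not show how a given attention or speech complaint would be coded, and some could fall under a listed term.

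**2. Bleeding list against the protocol**

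Sections 9.1.3 and 9.4 refer to intracranial bleeding without limit of site, and give no term list. The SAP counts three PTs. Whether any bleed would code elsewhere cannot be read from the documents. This half of the point is the weaker one.

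**3. Where an unlisted event would appear**

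- It appears in the AE tables by PT and by SOC and PT, and in the patient listing (SAP 4.7.1).
- An intracranial bleed also appears in the SAE tables.
- A cognitive event may appear in the dementia SMQ tables (SAP 4.7.3). Those are by PT, and the SMQ's content is not in the documents.
- It does not appear in the seven AESI category tables.

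SAP 4.7.1 counts a patient once per PT or once per SOC. PT rows cannot be added to a patient-level rate, because one patient may have several PTs. A SOC row pools the event with unrelated ones. So no planned table other than the AESI category tables gives a combined rate for either risk.

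**4. Direction**

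Take the broad definition to be the listed terms plus any others within the protocol's wording. A patient counted by the closed list is always counted by the broad one. The closed-list rate is therefore lower or equal, never higher.

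**5. Illustration of size (assumed inputs)**

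Let R be the rate under the broad definition and s the share of affected patients who have only unlisted PTs.

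- Listed rate = R × (1 − s)
- Patients missed = 230 × R × s, where 230 is the planned avapritinib arm

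For cognitive effects take R = 30%. This is the Phase 1 aggregate in Protocol 1.2.3.1 (0.30 × 116 = 34.8, about 35 patients). Its component terms are not stated, so equating it with the broad definition is an assumption, as is every value of s.

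| s | Listed rate | Missed of 230 |
|---|---|---|
| 0% | 30% | 0 |
| 10% | 0.30 × 0.90 = 27% | 230 × 0.30 × 0.10 = 6.9 |
| 25% | 0.30 × 0.75 = 22.5% | 230 × 0.30 × 0.25 = 17.25 |
| 50% | 0.30 × 0.50 = 15% | 230 × 0.30 × 0.50 = 34.5 |

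For bleeding, with R assumed at 1% to 3% and s at 0% to 50%, the number missed runs from 0 to 230 × 0.03 × 0.50 = 3.45 patients. The numbers are small, but so is the count they would be missing from.

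**The case against.** The strongest reply is that the two texts serve different purposes. The five-domain wording is a footnote to a table headed "Dose Modification and Re-escalation Guidelines for Avapritinib-Related Toxicity". The SAP category is called cognitive effects, without mood, and the follow-up rule in Protocol 9.4 speaks only of cognitive function. A broad trigger for dose management and a narrow reporting category can coexist. This stands to the extent that the SAP breaks no protocol AESI definition, since none exists. It does not explain the omission. Table 1 itself refers to events in that row group as the cognitive effect, and Protocol 6.3 uses the same short label for the guidance. The SAP's title therefore does not show that mood, speech and attention were left out on purpose, and no reason is given.

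The second reply is that nothing is lost: the AE, SAE and dementia tables and the listings carry these events, and QLQ-C30 cognitive and emotional functioning are summarised as well. That is right about visibility, but none of these outputs gives a category rate.

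Several stronger readings are tempting, and the documents do not support them:

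- A reader might infer that the rates will be under-counted. That happens only if some patient's sole event codes outside the lists, and no PT-level frequencies are given.
- A reader might take the 30% Phase 1 rate as evidence of size. It may rest on these same four terms.
- A reader might infer a biased combined discontinuation rate. The two discontinuation tables are by PT only, so no such rate is planned.
- A reader might infer a distorted comparison between arms. SAP 3.2.7 presents safety for all treatment groups, and the share of unlisted events in each group is unknown.

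**Conclusion.** The mismatch is real and should be resolved, though it concerns descriptive safety tables only. The cognitive list names no term for three of the five domains that the protocol groups together, and the bleeding list may not capture every intracranial bleed. As written, a patient whose only event falls outside the lists is left out of the only planned patient-level category rates for that risk.

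The possible error is downward or zero. Its size cannot be derived from the documents, and the 27% to 15% range rests wholly on assumed values of R and s. The conclusion assumes that the AESI categories are meant to describe the same risks as Table 1 and Protocol 9.1.3 and 9.4. If a narrower scope was intended, the SAP should say so and give the reason.

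**What to change.** Amend SAP 4.7.2 before unblinding:

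- Define the cognitive category by a medically reviewed PT list covering all five domains of Table 1, footnote 1. Alternatively, keep the cognitive category and add a separate one for the remaining domains, with a combined patient-level row.
- Define intracranial bleeding by all PTs for haemorrhage at any intracranial site, for example through a standard MedDRA grouping.
- Keep the present 4- and 3-term lists as a narrow sensitivity display.

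The cost is one term review, a short SAP edit and some extra table rows. The downside for the sponsor is that the stated AESI rates may be higher. Timing matters, because a list extended after treatment-level results are known would look data-driven.

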## **Avapritinib**

### **Statistical Analysis Plan Study BLU-285-1303**

- Grade 3/4/5 AESI related to study drug by AESI category and PT
- AESI by AESI category, PT, and NCI CTCAE Grade
- AESI leading to permanent discontinuation of study drug by PT
- AESI related to study drug leading to permanent discontinuation of study drug by PT

#### **4.7.3 Dementia Adverse Events**

Dementia adverse events will be summarized using MedDRA Dementia SMQ PTs. The general rules for summarizing AE specified in [Section 4.7.1](#) apply for dementia AE for avapritinib. The following dementia AE tables will be presented:

- Dementia AE by PT
- Dementia AE related to study drug by PT
- Serious Dementia AE by PT
- Serious Dementia AE related to study drug by PT
- Grade 3/4/5 Dementia AE by PT
- Grade 3/4/5 Dementia AE related to study drug by PT
- Dementia AE by PT and NCI CTCAE Grade
- Dementia AE related to study drug by PT and NCI CTCAE Grade
- Serious Dementia AE by PT and NCI CTCAE Grade
- Serious Dementia AE related to study drug by PT and NCI CTCAE Grade

**Avapritinib**  
**Statistical Analysis Plan Study BLU-285-1303**

**Table 4: Summary of Adverse Event Tables:**

Safety Endpoint	Main Table	by PT		by SOC, PT		by PT, CTCAE	by SOC, PT, CTCAE
		Overall	Subgroup	Overall	Subgroup	Overall	Overall
Summary Table (each item below one row)	X						
AE		X	X	X	X	X	X
SAE		X	X	X	X	X	X
Grade 3+ AE		X	X	X	X		
Related AE		X	X	X	X	X	X
Related SAE		X	X	X	X	X	
Related Grade 3+ AE		X	X	X	X		
AE Leading to Permanent Study Discontinuation		X		X			
Related AE Leading to Permanent Study Discontinuation		X					
AE Leading to Dose Interruption		X		X			
Related AE Leading to Dose Interruption		X					
AE Leading to Dose Reduction		X		X			
Related AE Leading to Dose Reduction		X					
Listing (Death, Discontinuation, SAE)	X						
AESI by Category and		X				X	
Related AESI by Category and		X					
Serious AESI by Category and		X					
Related Serious AESI by Category and		X					
Grade 3+ AESI by Category and		X					
Related Grade 3+ AESI by Category and		X					
AESI Leading to Permanent Study Discontinuation		X					
Related AESI Leading to Permanent Study Discontinuation		X				X	
Dementia AE		X				X	
Related Dementia AE		X				X	

**Avapritinib**  
**Statistical Analysis Plan Study BLU-285-1303**

Serious Dementia AE		X				X	
Related Serious Dementia AE		X				X	
Grade 3+ Dementia AE		X					
Related Grade 3+ Dementia AE		X					

#### **4.7.4 Deaths**

On treatment deaths will be summarized by treatment group by SOC and PT.

A listing of patients who died will be provided specifying the date of death, the cause of death, and the date of last dose of study drug. On treatment deaths, defined as deaths which occur between the first dose date of study drug to last dose date of study drug during the relevant study treatment period + 30 days, will be clearly marked.

#### **4.7.5 Clinical Laboratory Evaluations**

The central laboratory parameters with both baseline and post-baseline assessments will be summarized by treatment group and scheduled visit for the Safety Population. If there are multiple values recorded for a specific visit, then the last reported value will be used for that visit. Baseline is defined as the last assessment prior to start of study treatment. Data will be presented in Standard International units.

Clinical laboratory values will be graded according to NCI CTCAE version 4.03 or 5.0 for applicable parameters. Shift tables of laboratory data from baseline to worst grade during treatment, including unscheduled visits, will be presented. For laboratory parameters (including hemoglobin, glucose, sodium, potassium, magnesium, glucose, bilirubin, and phosphate), shift tables in maximum CTCAE grades of worst high and worst low assessment will be presented separately.

Overall summary and changes from baseline will be presented for hematology and serum chemistry (including coagulation) laboratory values.

Listings will be provided for each laboratory parameter. All results outside predefined normal ranges and CTCAE grade will be flagged in the data listings.

Urinalysis will be presented in listing only.

Boxplots of selected lab tests (including leukocytes, neutrophils, platelets, hemoglobin, alanine aminotransferase, aspartate aminotransferase, alkaline phosphatase, total bilirubin, and phosphate) values will be presented by visit.

Local laboratory tests will be listed only, with the exception of the shift tables, which will include both central and local results when deriving the worst grade.

